6.2. TIME POINT CONVENTIONS

6.2.1. START OF TREATMENT CONVENTIONS

Subjects enrolled in Part 1 of the study will receive a single oral, 400 mg dose of tazemetostat on Day 1. Subjects enrolled in Part 2 of the study will receive a single, oral, 800 mg dose of tazemetostat on Day 1. Calculations relative to start of study treatment will depend on the context of the analysis. The following rules will apply:

Analysis Category	Reference Start Date
Demographics, Baseline Characteristics, and Medical History	Date of first dose of any study drug
Safety Measures and Non-Study Medications	Unless noted otherwise, date of first dose of any study drug
Tazemetostat Exposure and Compliance	Date of first dose of tazemetostat

Depending on the context, listings may present assessments in terms of 'Study Day'. For consistency with the protocol, the first day of any study treatment will be identified as 'Day 1'. Assessments performed the day prior to the first day of study treatment will be identified as 'Day -1' (with no intervening 0). Study Day will be calculated as follows:

- Assessment date is on/after first dose date of study drug:
Study Day = (date of event – first dose date of study drug) + 1

-
- Assessment date is prior to first dose date of study drug:
Study Day = (date of event – first dose date of study drug)
 - The assessment date is greater than last date of study drug:
Post Tx Study Day = (date of event – last dose date)

In these cases, Study Day will be displayed as “## days post tx”.

For partial dates, Study Day will be missing in the listings. Further information about partial date conventions is described in [Appendix 1](#).

6.2.2. BASELINE ASSESSMENTS

Baseline data are defined as the last non-missing assessment (including unscheduled assessments) prior to starting treatment. If there is more than one value on or prior to starting treatment, the value closest to and prior to the receipt of the first dose, whether scheduled or unscheduled, will be used as the baseline value. Unless the collection time or label indicates otherwise, assessments performed on the same day as the first dose of study drug will be considered performed prior to the start of treatment. AEs and medications reported with a start date on the date of first dose will be considered to have occurred after the start of treatment. For vital signs (excluding weight and height) and ECG measures, baseline results will be identified for the set.

For laboratory parameters, the baseline time point will be determined separately for each parameter.

6.2.3. VISIT ASSESSMENTS AND STUDY DAY CONVENTIONS

For by visit summaries, nominal visits will be presented (i.e. visit windowing will not be applied). Unless otherwise specified, unscheduled measurements will not be included in by-visit summaries but will contribute to worst-case values where required (eg. shift table). Listings will include both scheduled and unscheduled data.

6.2.4. END OF TREATMENT ASSESSMENT

Wherever an end-of-treatment assessment result is required for analysis, the last non-missing assessment result within 30 days after the final dose of study drug or until the start of a subsequent anticancer therapy, whichever is earlier, will be used.

6.2.5. MISSING DATA

Unless otherwise specified, missing data will be treated as missing, i.e., no special handling will be performed. Details of safety data handling will be documented in safety analyses section.

6.2.6. PARTIAL/MISSING DATES

For partial dates, the algorithms for imputation will vary depending upon the parameter; missing or incomplete medications start and stop dates will be imputed to determine whether the medications are taken prior to the study drug or concomitantly. Missing adverse event (AE) start dates will be imputed to determine whether the AEs are treatment emergent. In listings, all dates will be listed as recorded. The details of imputation algorithm rules can be found in [Appendix 1](#).

6.3. UNIT CONVENTIONS

- 1 year = 365.25 days. Year is calculated as (days/365.25) and will be rounded to 1 digit after the decimal point (tenths) for presentation purposes.
- 1 month = 30.4375 days. Month is calculated as (days/30.4375) and will be rounded to 1 digit after the decimal point (tenths) for presentation purposes.
- 1 pound = 0.454 kg and 1 kg = 2.2 pounds.
- 1 inch = 2.54 cm and 1 cm = 0.3937 inches.
- Body mass index (BMI) calculated as [weight (kg)/height (m)²]
- BMI calculated as [weight (lb) / height (in)²] x 703
- Unless otherwise specified, percentages will be calculated based on the number of subjects specified by the appropriate analysis population definition.
- All tables, listings, figures will be produced in landscape orientation using the default Courier New 9-point font whenever feasible. Output files will be created in rich text file (RTF) format.

7. STATISTICAL CONSIDERATIONS

Unless noted otherwise, the statistical considerations below will be applied and used for both study parts.

- As this is a phase I study, data from all centers will be pooled for analyses.
- Unless otherwise noted, table summaries will be presented by study part and overall.
- The issue of multiplicity will not apply to the endpoints for this study.
- Except for incomplete dates associated with AEs and medications (rules in [Appendix 1](#)) and missing severity or relationship (rules in Section 16.1), other missing safety data will not be imputed.
- Summary statistics will consist of the number and percentage of subjects in each category for discrete variables, and the number of subjects with non-missing values, mean, median, standard deviation (SD), minimum, and maximum for continuous variables.
- When the denominator includes subjects with missing values, a “missing” category may be added for completeness.
- In summary tables of continuous variables (except for weight, height and BMI), the minimum and maximum values will be displayed to the same number of decimal places as the raw data; all mean, median, and percentile values will be formatted to one more decimal place than the measured value. SD values will be formatted to two more decimal places than the measured value, unless otherwise specified. The maximum number of decimal places is 3 and values will be truncated to 3 decimal places in situations where there are more than 3 decimal places. Wherever possible data will be decimal aligned. For weight, height and BMI, only one decimal place will be kept for summary results (except N).

- All percentages will be rounded to one decimal place. The number and percentage of responses will be presented in the form XX (XX.X%).
- Change from baseline = test value at the post-baseline visit – baseline value. The percentage change from baseline will be calculated as (test value at the post-baseline visit - baseline value)/baseline value x 100. Percent of baseline is calculated as test value at the post-baseline visit/baseline value x 100. If either the baseline or the post-baseline value is missing, the change from baseline, percentage change from baseline, and percent of baseline are set to missing. If baseline is 0, then percentage of baseline and percentage change from baseline are set to missing.
- Post Baseline Duration in days = end date – start date + 1 (divide by 7 to convert to weeks, divide by 30.4375 to convert to months, and divide by 365.25 to convert to years; round result to 1 decimal place)
- Listings typically will be sorted by study part, subject identification number (concatenated site and subject number), visit, date, and time, if collected.
- P-values, if applicable, will be presented to 3 decimal places. If the rounded result is a value of 1.000, it will be displayed as > 0.999.
- Any date in the listings will use the *date9.* format, for example, 07MAY2002.
- All analyses will be conducted with SAS version 9.4 or higher.

8. SUMMARY OF ANALYSIS POPULATIONS AND ENROLLMENT

The number of subjects in each analysis population (Enrolled, Safety and PK populations) will be summarized by study part and overall on the Enrolled population.

A subject listing indicating analysis population, study part, and site of enrollment will be presented.

9. DISPOSITION

Study disposition will be summarized by study part and overall. A summary of subject disposition will include number and percentages for the following categories:

- Subjects in each defined analysis population
- Subjects who discontinued study treatment and reason for discontinuation
- Subjects who withdraw from study and reasons for withdrawal
- Subject replacements and reasons for replacements, if any.

10. MAJOR PROTOCOL DEVIATIONS

All protocol deviations will be listed for the safety population. Protocol deviations will be summarized by major and minor category and by study part. Predefined categories of major protocol deviations will include:

- Violation of inclusion/exclusion criteria

-
- Prohibited medications
 - Study drug compliance

Additional categories may be added during the course of the study but will be determined prior to database lock.

11. DEMOGRAPHIC AND OTHER BASELINE CHARACTERISTICS

Demographic data and other baseline characteristics will be summarized by study part and overall, and listed for the Enrolled population. Demographics will include age (derived, in years), sex, race, ethnicity, and baseline characteristics will include, but not limited to, Eastern Cooperative Oncology Group (ECOG) performance status, complete physical examination, vital signs and drug/alcohol screening details.

Baseline disease characteristics will include tumor diagnosis (TD), prior anticancer therapy (yes/no), prior radiotherapy (yes/no), prior cancer related surgery (yes/no), progressive disease prior to study entry (yes/no), prior disease progression date of last progression prior to the study enrollment, blood smear (BS), Bone Marrow Aspirate/Biopsy (BM) and time from date of last disease progression to study entry (in months).

12. SURGICAL AND MEDICAL HISTORY

Surgical and medical history occurring prior to start of study treatment will be summarized and listed for the Enrolled population.

Medical and surgical history will be coded using the Medical Dictionary for Regulatory Activities (MedDRA) v23.1. The number and percentage of subjects with any surgical and medical history will be summarized. Medical history also will be summarized by MedDRA system organ class (SOC) and preferred term (PT). Surgical history will be summarized by the MedDRA high-level group term (HLGT) and PT. Listings will include start date and stop date or notation of ongoing for conditions continuing into the study treatment period.

13. MEDICATIONS

Medications will be coded using World Health Organization (WHO) Drug Dictionary version September 2020. For incidence summaries of medications coded by WHO Anatomical Therapeutic Chemical (ATC) category, a subject will be counted once even if the subject took more than one medication within a specific ATC category (likewise for PT).

13.1. PREVIOUS ANTICANCER THERAPIES

Previous anticancer therapy and radiotherapy will be summarized and listed for the Enrolled population. The summary for previous anticancer therapies will include:

- Number of regimens (descriptively and by category (1, 2, 3, 4, or more than 4 prior regimens))
- History of any prior therapy by setting (Neoadjuvant, Adjuvant, Therapeutic for

Advanced/Metastatic Disease, Consolidation, Maintenance, Palliation, or Unknown); A subject may be counted in multiple categories

- Incidence of prior anticancer therapies by WHO Drug ATC level 4 and PT

The summary for the previous radiotherapy will include:

- Number of prior courses (0, 1, or 2 or more courses)
- Major sites of prior radiotherapy (subdivisions of those sites will be listed); A subject may be counted in multiple categories

The summary for prior transplant will include:

- Incidence of prior transplant (autologous or allogenic)
- Type of prior autologous transplant (bone marrow, peripheral blood stem cell, or both)

13.2. PRIOR AND CONCOMITANT MEDICATIONS

Medications will be summarized and listed for the Safety population. Summary tables will include incidence (number and percentage) of subjects receiving any medication and incidence of specific medications by WHO Drug ATC level 4 and PT.

Prior and concomitant medications will be summarized separately. Categorization will be defined as follows:

- Prior medications will include medications which stopped prior to the first dose of study drug.
- Concomitant medications are defined as medications that were started at any time after the start of first dose of study drug and stopped prior to the end of study treatment or the discontinuation of study drug, whichever is earlier.
- Medications that started prior to the first dose of study drug and continued into study treatment period until the end of study treatment or the discontinuation of study drug, whichever is earlier, are considered as both prior and concomitant.
- Post-treatment medications will include anticancer therapies which started after discontinuation of study drug.

Medications with missing or partially missing start or end dates will be handled according to the conventions described in Appendix 1. If it cannot be determined whether a medication was a prior medication due to partial medication start date or end date, the medication will be considered concomitant. If medication start date and end date are missing, the medication will be considered concomitant. Prohibited medications, as defined in Section 9.3 of the protocol, will be identified with a '*' in the listing.

14. STUDY DRUG EXPOSURE AND COMPLIANCE

Study drug exposure and compliance will be summarized and listed for the Safety population.

14.1. STUDY DRUG EXPOSURE

The following summaries of study drug exposure will be presented:

Study Parts 1 and 2:

- Duration of tazemetostat exposure (weeks)

Duration of exposure (weeks) = [(date of last actual dose of tazemetostat – date of first dose of tazemetostat) + 1]/7.

Except for the first and last dose dates, this calculation is not adjusted for periods where dosing is interrupted or dose is recorded as 0.

- Duration of Exposure Category

Part 1	Part 2

 - Days 1-39 (Weeks 1-5.6) - Days 40-67 (Weeks 5.7-9.6) - Days 68-95 (Weeks 9.7-13.6) - Days 96-123 (Weeks 13.7-17.6) - Days 124-151 (Weeks 17.7-21.6) - 	
 - Days 1-26 (Weeks 1-3.7) - Days 27-54 (Weeks 3.8-7.7) - Days 55-82 (Weeks 7.8-11.7) - Days 83-110 (Weeks 11.8-15.7) - Days 111-138 (Weeks 15.8-19.7) -

- Total number of cycles of study drug tazemetostat administered, categorized as follows.
 - 1) **Part 1:** Cycle 1 starts on day 1 and finishes on day 39, and Cycle 2 will begin on day 40 (Cycle 2 day 1) and each subsequent cycle from Cycle 2+ onwards will be of 28-day duration.
 - 2) **Part 2:** Cycle 1 starts on day 1 and finishes on day 26, and Cycle 2 will begin on day 27 (Cycle 2 day 1) and each subsequent cycle from Cycle 2+ onwards will be of 28-day duration.

Part 1	Part 2

 - Cycle 1 (Days 1-39; Weeks 1-5.6) - Cycle 2 (Days 40-67; Weeks 5.7-9.6) - Cycle 3 (Days 68-95; Weeks 9.7-13.6) - Cycle 4 (Days 96-123; Weeks 13.7-17.6) - Cycle 5 (Days 124-111; Weeks 17.7-21.6) - 	
 - Cycle 1 (Days 1-26; Weeks 1-3.7) - Cycle 2 (Days 27-54; Weeks 3.8-7.7) - Cycle 3 (Days 55-82; Weeks 7.8-11.7) - Cycle 4 (Days 83-110; Weeks 11.8-15.7) - Cycle 5 (Days 111-138; Weeks 15.8-19.7) -

- Total amount of tazemetostat taken (mg) for Cycle 1 and all subsequent cycles, separately.
- Average dose intensity of tazemetostat:

Part 1:

- 1) For Cycle 1 (Days 1-39):
 - Average dose intensity (mg BID/day) = total amount of tazemetostat taken (mg) / (2*30) (days) (mg BID/day)
 - Planned average dose intensity (mg BID/day) = $[400*3+400*2*(12+15)]/(2*30) = 22,800/(2*30)=380$ (mg BID/day)
- 2) For Cycle 2 + onwards

Average dose intensity (mg BID/day) = total amount of tazemetostat taken (mg) / [2 * duration of exposure (days)] (mg BID/day)
 where duration of exposure (days) = [(date of last actual dose of tazemetostat – date of first dose of tazemetostat) + 1] (days)

Part 2:

1) For Cycle 1 (Days 1-26):

- Average dose intensity (mg BID/day) = total amount of tazemetostat taken (mg) / (2* 22) (days) (mg BID/day)
- Planned average dose intensity (mg BID/day) = $[800*3+800*2*(12+7)]/(2*22) = 32,800/(2*22) = 745.45$ (mg BID/day)

2) For Cycle 2+ onwards

Average dose intensity (mg BID/day) = total amount of tazemetostat taken (mg) / [2 * duration of exposure (days)] (mg BID/day)
 where duration of exposure (days) = [(date of last actual dose of tazemetostat – date of first dose of tazemetostat) + 1] (days)

- For assessment of tolerability, numbers of subjects requiring dose reductions, treatment interruption or treatment discontinuation in response to AEs (based on action taken for reported AEs)

The following summaries of study drugs itraconazole in part 1 and rifampin in part 2 will be presented.

Study Part 1:

- Summary statistics for the total amount of itraconazole received (mg)
- Number (%) of subjects who received <4200 mg, 4200 mg and > 4200 mg of itraconazole

Study Part 2:

- Summary statistics for the total amount of rifampin received (mg)
- Number (%) of subjects who received < 5400 mg, 5400 mg and > 5400 mg of rifampin

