7.2. Number of Subjects

Approximately 40 subjects will be enrolled in the study assuming about a 40% drop out rate to achieve 12 subjects who complete each part of the study for a total of 24 completed subjects. Subjects will complete either Part 1 or Part 2, but not both.

Subjects who require a tazemetostat dose interruption or reduction during Cycle 1 of either Part 1 or Part 2 will be replaced. During Cycle 1, subjects who miss two or more consecutive tazemetostat/itraconazole/rifampin doses or more than three tazemetostat/itraconazole/rifampin doses in total will be replaced. Subjects who miss two or more consecutive PK blood sample collections during either part of Cycle 1 will be replaced. Subjects that require replacement will be discontinued from study treatment.

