4.2. SAMPLE SIZE

The sample size was determined based on feasibility considerations. Approximately 40 subjects will be enrolled in the study assuming about a 40% drop out rate to achieve 12 subjects per study part for a total of 24 completed subjects. Subjects will complete either Part 1 or Part 2, but not both.

Subjects who require a tazemetostat dose interruption or reduction during Cycle 1 of either Part 1 or Part 2 will be replaced. During Cycle 1, subjects who miss two or more consecutive tazemetostat/itraconazole/rifampin doses or more than three tazemetostat/itraconazole/rifampin doses in total will be replaced. Subjects who miss two or more consecutive PK blood sample collections during either part of Cycle 1 will be replaced. Subjects that require replacement will be discontinued from study treatment.

A total of 12 subjects per study part is adequate to describe the effect of CYP3A4 inhibition by itraconazole or induction by rifampin on the steady state PK of tazemetostat.

A point estimate and associated 90% confidence interval on the magnitude of the effect of the perpetrator drugs on the PK of the victim drugs will be provided. The default no effect boundary of 80 – 125% for the 90% confidence interval for an effect size will be used as a reference. This is equivalent to a hypothesis test with a null hypothesis that there is a nonzero effect and alternative of no effect. If the 90% confidence interval for any effect tested in this study falls completely within 80 – 125%, it will be concluded that no significant differences are present.

The sample size calculation is based on the underlying assumption that the within subject coefficient of variation (CV) is 30%, a two-sided alpha level of 0.05, the underlying within-subject correlation of subsequent measurements of the same PK parameter and geometric mean ratio. If the geometric mean ratio of itraconazole is 1.06 or the geometric mean ratio for rifampin is 0.94 and subsequent measurements of tazemetostat AUC have a correlation of at least 0.80, this test is powered at 88% or higher.

Calculations were performed using the Paired t-test for the Equivalence of Log-Normal Means (Multiplicative Model) in nQuery version 8.0.

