14.2. STUDY DRUG COMPLIANCE

The following summaries of study drug compliance will be presented for Cycle 1 and all subsequent cycles, separately:

- Percentage tazemetostat taken (summarized as a continuous variable).

Study Part 1:

Cycle 1: Percentage of tazemetostat taken = $100\% \times \text{Average dose intensity (mg BID/day)} / \text{Planned average dose intensity (mg BID/day)}$.

Cycle 2+: Percentage of tazemetostat taken = $100\% \times \text{Average dose intensity (mg BID/day)} / 800 \text{ mg BID/day}$.

Study Part 2:

Cycle 1: Percentage of tazemetostat taken = $100\% \times \text{Average dose intensity (mg BID/day)} / \text{Planned average dose intensity (mg BID/day)}$.

Cycle 2+: Percentage of tazemetostat taken = $100\% \times \text{Average dose intensity (mg BID/day)} / 800 \text{ mg BID/day}$.

- Category of percentage of tazemetostat taken (using categories $\geq 90\%$, 80% to $< 90\%$, 70% to

< 80%, and < 70%).

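### Cycle 1 tazemetostat compliance is scored against the full planned cycle for every subject, so early discontinuation is counted as missed doses

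*SAP*

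**What the plan says.** SAP 14.1 gives Cycle 1 dose intensity a fixed divisor. Part 1 reads "Average dose intensity (mg BID/day) = total amount of tazemetostat taken (mg) / (2*30) (days) (mg BID/day" and Part 2 reads "Average dose intensity (mg BID/day) = total amount of tazemetostat taken (mg) / (2* 22) (days) (mg BID/day". The planned intensities use the same divisors: 22,800/(2×30) = 380 for Part 1, and "32,800/(2*22) = 745.45" for Part 2.

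SAP 14.2, headed as study drug compliance, takes the ratio of the two. It reports "Percentage tazemetostat taken (summarized as a continuous variable" and also in four bands (90% or more, 80% to under 90%, 70% to under 80%, under 70%). SAP 14 applies this to the Safety population. Nothing restricts it to subjects who completed Cycle 1 or prorates it for those who did not.

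For Cycle 2+ the divisor is twice the subject's own exposure time, "where duration of exposure (days) = [(date of last actual dose of tazemetostat – date of first dose of tazemetostat) + 1] (days".

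Two other provisions bear on this. SAP 4.2 expects many early leavers: "Approximately 40 subjects will be enrolled in the study assuming about a 40% drop out rate to achieve 12 subjects per study part". Protocol 7.5.1 allows no tazemetostat interruption or reduction in Cycle 1; a subject who needs one is taken off treatment and replaced.

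**The concern.** A compliance figure should say how much of the drug due to be taken was taken. Once a subject has been discontinued, no further doses are due. The Cycle 1 formula still counts every later dose as not taken, so a subject who took each dose until withdrawal looks the same as one who stayed on treatment and skipped doses.

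In this trial that will not be rare. About 40% dropout is planned, and any need to interrupt or reduce in Cycle 1 ends treatment under the protocol. The same heading and bands then cover Cycle 2+, where the denominator does follow the subject's own time on drug, so the two figures are not comparable. A reader of the study report could take a sizeable low band in Cycle 1 as poor adherence when some or all of it is early exit.

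**Working it through.** **Inputs.** Dosing days from Protocol 7.3; divisors and planned totals from SAP 14.1; bands from SAP 14.2; dropout from SAP 4.2.

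**Reproducing the SAP's planned figures.**
- Part 1: single doses on Days 1, 15 and 36, twice daily on Days 3–14 (12 days) and 21–35 (15 days). Doses = 3 + 2 × 27 = 57. Amount = 57 × 400 = 22,800 mg. Intensity = 22,800/60 = 380.
- Part 2: single doses on Days 1, 15 and 24, twice daily on Days 3–14 (12 days) and 17–23 (7 days). Doses = 3 + 2 × 19 = 41. Amount = 41 × 800 = 32,800 mg. Intensity = 32,800/44 = 745.45.

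Both agree with the SAP.

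**Reducing the compliance formula.** Part 1: (mg taken/60) ÷ (22,800/60) = mg taken/22,800 = doses taken/57. Part 2: (mg taken/44) ÷ (32,800/44) = mg taken/32,800 = doses taken/41. Time on treatment does not enter.

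**Fully adherent subject who stops early.** Doses through Day 15 = 1 + 12 × 2 + 1 = 26 in both parts.

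| Last dose | Doses taken | SAP score | Against doses scheduled to that point |
|---|---|---|---|
| Part 1, Day 15 | 26 | 26/57 = 45.6% | 100% |
| Part 1, Day 27 morning | 39 | 39/57 = 68.4% | 100% |
| Part 1, Day 27 evening | 40 | 40/57 = 70.2% | 100% |
| Part 1, Day 33 evening | 52 | 52/57 = 91.2% | 100% |
| Part 1, Day 35 evening | 56 | 56/57 = 98.2% | 100% |
| Part 2, Day 15 | 26 | 26/41 = 63.4% | 100% |
| Part 2, Day 17 evening | 28 | 28/41 = 68.3% | 100% |
| Part 2, Day 18 morning | 29 | 29/41 = 70.7% | 100% |
| Part 2, Day 22 morning | 37 | 37/41 = 90.2% | 100% |
| Part 2, Day 23 evening | 40 | 40/41 = 97.6% | 100% |

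The score is below 70% at 39 of the 56 possible early exit points in Part 1 and 28 of 40 in Part 2. The 90% band is first reached on the evening of Day 33 (Part 1) or the morning of Day 22 (Part 2).

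**Effect on the table (illustration only).** The documents give neither the timing of dropout nor its split between parts. Suppose 8 of 20 subjects in each part stop after the Day 15 dose and nobody misses a dose. Mean compliance would read (12 × 100 + 8 × 45.6)/20 = 78.2% in Part 1 and (12 × 100 + 8 × 63.4)/20 = 85.4% in Part 2, with 40% of subjects under 70%, although adherence is complete.

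**Testing the remedy.** Suppose a subject misses the Day 11 evening and Day 12 morning doses and is then discontinued. Scheduled doses = 1 + 9 × 2 + 1 = 20; taken = 18. The SAP now gives 18/57 = 31.6% or 18/41 = 43.9%. A prorated denominator gives 18/20 = 90.0%, the top band. Proration alone would therefore put some subjects replaced for missed doses among the most compliant, so the replacement criteria need to be shown beside it.

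**The case against.** The strongest defence is that Cycle 1 is a fixed regimen with no modification allowed, so percent of the planned dose is a natural summary, and the SAP does name the variable percentage taken. Cycle 2+ is open-ended and cannot have a fixed total, so some difference in denominators is to be expected. Other planned outputs (discontinuation and replacement reasons in SAP 9, exposure duration and total mg in SAP 14.1, subject listings) let a careful reader separate early exit from missed doses. All of this stands, and it keeps the point small. It does not correct a table headed compliance whose figure is not adherence.

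A reader might infer more than the documents support:
- *That every fully adherent early leaver falls under 70%.* Only exits up to the dates shown above do.
- *That the 16 of 40 subjects implied by 40% dropout will be mis-scored, all for progression or toxicity.* The documents give no reasons or timing. Sixteen is a ceiling, and some leavers may have been replaced for missed doses, for whom a low score is not misleading.
- *That the fixed denominator lets subjects meeting the rule "more than three tazemetostat/itraconazole/rifampin doses in total will be replaced" score 90% or more.* A subject who reaches the end of Cycle 1 with four missed doses scores 53/57 = 93.0% or 37/41 = 90.2% under either denominator. That comes from the band limits. Replaced subjects are also to be discontinued, so under the present formula a high score needs a trigger in the last days of dosing or one detected late.

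**Conclusion.** The point holds as a minor error in a descriptive summary. Cycle 1 compliance is the share of the full planned cycle dose received, and it understates adherence for every fully adherent subject who stops early: 45.6% or 63.4% after a Day 15 exit, below 70% for exits through the morning of Day 27 (Part 1) or the evening of Day 17 (Part 2), and 70% to 98% after that. These figures rest only on the dosing schedule and the SAP's formulas. How many subjects are affected depends on dropout timing, which the documents do not give.

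Two wider consequences might be inferred and are not shown. SAP 10 lists study drug compliance as a major-deviation category but does not say that this percentage defines it. No primary or secondary endpoint or analysis population is stated to use the percentage, and the PK analysis is left to a separate plan, so an effect on the interaction estimate cannot be claimed.

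**What to change.** In SAP 14.1 and 14.2, for Cycle 1:

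1. Define compliance as tazemetostat taken divided by tazemetostat scheduled from Day 1 to the subject's treatment discontinuation, or to the end of Cycle 1 for completers, leaving out the planned no-dose days. End the period at discontinuation and not at the last dose taken; otherwise doses missed just before stopping vanish (18/18 instead of 18/20 in the example above).
2. Keep mg taken over 22,800 or 32,800, labelled as percent of planned Cycle 1 dose received.
3. Beside the compliance bands, report the number of subjects meeting the protocol's existing missed-dose replacement criteria: two or more consecutive doses, or more than three in total, counting tazemetostat and itraconazole or rifampin. A simple count of missed tazemetostat doses would not do, because it overlooks the consecutive-dose trigger and the other two drugs.

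Fully adherent early leavers then score 100%, and completers' scores do not change. The cost is a few lines of SAP text and a small programming change. The protocol already asks for given, missed and vomited doses to be recorded, and the SAP already plans summaries of discontinuation and replacement.

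### As written, the Cycle 2+ dose-intensity denominator in SAP 14.1 counts Cycle 1 days, so a fully adherent subject scores 41.8% (Part 1) or 51.9% (Part 2) after one Cycle 2+ cycle instead of 100%

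*SAP*

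**What the plan says.** SAP 14.1 opens with whole-study exposure: "Duration of exposure (weeks) = [(date of last actual dose of tazemetostat – date of first dose of tazemetostat) + 1]/7". It then asks for "Total amount of tazemetostat taken (mg) for Cycle 1 and all subsequent cycles, separately", and gives average dose intensity in two blocks per part, one for Cycle 1 and one for Cycle 2 onwards.

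- **Cycle 1** has a fixed divisor. In Part 1: "Average dose intensity (mg BID/day) = total amount of tazemetostat taken (mg) / (2*30) (days) (mg BID/day"). Part 2 uses 2*22.
- **Cycle 2 onwards**, in both parts, divides the amount by twice the duration of exposure, "where duration of exposure (days) = [(date of last actual dose of tazemetostat – date of first dose of tazemetostat) + 1] (days"). Neither date is tied to a cycle.

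For the category of tazemetostat exposure and compliance, SAP 6.2.1 gives the reference start date as "Date of first dose of tazemetostat". It also says: "Calculations relative to start of study treatment will depend on the context of the analysis".

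SAP 14.2 divides the Cycle 2+ intensity by 800 mg BID/day to get a percentage taken. It begins: "The following summaries of study drug compliance will be presented for Cycle 1 and all subsequent cycles, separately". The result is summarised as a continuous variable and also under "Category of percentage of tazemetostat taken", with bands of at least 90%, 80% to below 90%, 70% to below 80%, and below 70%.

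**The concern.** The numerator and denominator of the Cycle 2+ ratio cover different periods. The amount excludes Cycle 1, because amounts and compliance are to be shown separately for Cycle 1 and later cycles. The duration includes Cycle 1, because its date expression is the whole-study one and 6.2.1 starts it on Day 1. Cycle 1 is 39 days in Part 1 and 26 days in Part 2, so a large block of days enters the denominator with no matching drug in the numerator.

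The percentage is then compared with 800 mg BID/day as if it measured adherence. A subject who missed nothing would be reported as poorly compliant. The shortfall also depends on time on treatment, being largest for those who stop soon after Cycle 2 begins, so the summaries would mix adherence with treatment length. It differs between parts as well, and SAP 6.1 asks for presentation by part and overall.

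**Working it through.** **The plan's own figures.** SAP 14.1 gives no worked Cycle 2+ value, but its planned Cycle 1 values reproduce:

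- Part 1: 400*3 + 400*2*(12+15) = 22,800 mg; 22,800/(2*30) = 380 mg BID/day.
- Part 2: 800*3 + 800*2*(12+7) = 32,800 mg; 32,800/(2*22) = 745.45 mg BID/day.

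**Inputs for Cycle 2+.**

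- Dose: 800 mg twice daily, or 1,600 mg/day (Protocol Table 3 and Table 4 footnotes on multi-dose administration).
- Cycle 2 is Days 40-67 in Part 1 and Days 27-54 in Part 2; later cycles last 28 days (SAP 14.1).
- Length of Cycle 1, C1: 39 days in Part 1 and 26 days in Part 2.
- k = number of completed, fully adherent Cycle 2+ cycles.

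**Formula as written.** The Cycle 2+ amount is 1,600*28k mg. Days from first to last dose are C1 + 28k. The percentage taken is

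1,600*28k / [2*(C1 + 28k)] / 800 = 28k/(C1 + 28k).

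| k | Part 1 | Part 2 |
|---|---|---|
| 1 | 28/67 = 41.8% | 28/54 = 51.9% |
| 2 | 56/95 = 58.9% | 56/82 = 68.3% |
| 3 | 84/123 = 68.3% | 84/110 = 76.4% |
| 8 | 224/263 = 85.2% | 224/250 = 89.6% |
| 9 | 252/291 = 86.6% | 252/278 = 90.6% |

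**Bands.** Full adherence belongs in the top band of 14.2. As written, a Part 1 subject is below 70% through three Cycle 2+ cycles and a Part 2 subject through two. To reach 90%, 28k must be at least 0.9*(C1 + 28k), so k must be at least 9*C1/28. That is 12.5 in Part 1 (13 completed cycles) and 8.4 in Part 2 (9 completed cycles).

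**Start window.** The protocol notes to Figures 2 and 3 allow Cycle 2 to begin up to 3 days late. With a 3-day delay and k = 1, the values are 28/70 = 40.0% and 28/57 = 49.1%.

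**Denominator started at the first Cycle 2 dose.** 1,600*28k / (2*28k) / 800 = 100% in both parts for every k, with or without the 3-day delay. If the last dose is a morning dose on day d of Cycle 2+ treatment, the value is (2d-1)/(2d): 9/10 = 90.0% at d = 5 and 55/56 = 98.2% at d = 28.

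**The case against.** The best reply is that context already limits the formula to Cycle 2 onwards. It sits under a sub-heading for those cycles. The parallel Cycle 1 formula uses an equally unqualified total amount that can only mean the Cycle 1 amount, so sub-headings appear to set scope throughout. SAP 14.1 gives the Cycle 2 start days (40 and 27). The flat 800 mg BID/day benchmark makes sense in Part 1 only if the 400 mg Cycle 1 dosing and its dose-free days are left out. SAP 6.2.1 lets calculations depend on context. A programmer might also notice that perfect adherence scores 41.8% and correct it.

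Most of this stands as evidence of intent: a Cycle 2+ denominator was very probably meant. It does not change the written date term, which repeats the whole-study expression and matches the start date that 6.2.1 assigns to this category.

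Three stronger readings are tempting but unsupported:

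- A reader might infer that Cycle 1 drug also enters the numerator, making this a whole-study ratio. The requirement to report amounts and compliance separately for Cycle 1 and later cycles argues against that.
- A reader might infer that the SAP never says when Cycle 2 starts. It does, in the same section; the start is missing only from the formula.
- A reader might treat nine Cycle 2+ cycles as the rollover point in both parts. Rollover is set at nine cycles or longer on 800 mg twice daily, and Part 2 already uses that dose in Cycle 1, so eight Cycle 2+ cycles could arguably qualify there.

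**Conclusion.** The point holds as a minor error in a stated rule. Applied literally, SAP 14.1 understates Cycle 2+ dose intensity and compliance for every subject who continues: for full adherence, by 58.2 percentage points in Part 1 and 48.1 in Part 2 after one cycle (100 - 41.8 and 100 - 51.9), shrinking to 13.4 and 9.4 after nine (100 - 86.6 and 100 - 90.6). It puts fully adherent subjects in the wrong 14.2 band for up to 12 completed Cycle 2+ cycles in Part 1 and 8 in Part 2.

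These figures assume full adherence at 800 mg twice daily, Cycle 2 starting on Day 40 or Day 27, and both doses taken on the last day of a completed cycle. The number of subjects who will continue past Cycle 1 is not known from the documents.

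The effect is confined to descriptive Cycle 2+ dose-intensity and compliance summaries. Nothing here bears on the PK comparison or on the Cycle 1 calculations, which have their own fixed divisors.

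**What to change.** In the Cycle 2+ block of SAP 14.1, for both parts, replace the definition with:

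Cycle 2+ average dose intensity (mg BID/day) = tazemetostat amount taken from Cycle 2 Day 1 onward (mg) / [2 x (last tazemetostat dose date - first Cycle 2 tazemetostat dose date + 1)].

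Use this value for the Cycle 2+ percentage in 14.2, and state that it is calculated only for subjects with at least one Cycle 2 dose. Leave the whole-study duration in weeks as it is.

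The cost is one SAP line per part. No new data and no design change are needed, and it can be done when the SAP is finalised before database lock, as SAP Section 1 requires.
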